9.2 Demographics and Subject Disposition

Subject disposition will be listed for each study part. The demographic variables age, sex, race, ethnicity, country of enrolment, site ID, body weight, height and body mass index will be summarized and listed for each study part.

9.3 Pharmacokinetic Assessment

9.3.1 Pharmacokinetic Analysis

PK parameter estimates will be determined using non-compartmental procedures in validated software program (Phoenix WinNonlin Version 6.4.1 or later).

Plasma concentrations of baricitinib will be used to determine the following PK parameters, when possible:

Parameter	Units	Definition
AUC(0- t_{last})	ng.h/mL	area under the concentration versus time curve from time zero to time t_{last} , where t_{last} is the last time point with a measurable concentration
AUC(0- ∞)	ng.h/mL	area under the concentration versus time curve from time zero to infinity
%AUC($t_{last}-\infty$)	%	percentage of AUC(0- ∞) derived by extrapolation
C_{max}	ng/mL	maximum observed drug concentration
t_{max}	h	time of maximum observed drug concentration
$t_{1/2}$	h	apparent terminal half-life
CL/F	L/h	apparent clearance
V_z/F	L	apparent volume of distribution during the terminal phase
V_{ss}/F	L	apparent volume of distribution at steady state

An alternative AUC measure, such as AUC to a common time point, may be calculated if AUC(0- ∞) cannot be reliably calculated.

Additional PK parameters may be calculated, as appropriate. The software and version used for the final analyses will be specified in the CSR. Any exceptions or special handling of data will be clearly documented within the final study report.

Formatting of tables, figures and abbreviations will follow the Eli Lilly Global PK/PD/TS Tool: NON-COMPARTMENTAL PHARMACOKINETIC STYLE GUIDE. The version of the tool effective at the time of PK analysis will be followed.

General PK Parameter Rules

- Actual sampling times will be used in the final analyses of individual PK parameters, except for predose sampling times which will be set to zero.
- C_{max} and t_{max} will be reported from observed values. If C_{max} occurs at more than one time point, t_{max} will be assigned to the first occurrence of C_{max} .
- AUC parameters will be calculated using a combination of the linear and logarithmic trapezoidal methods (linear-log trapezoidal rule). The linear trapezoidal method will be applied up to t_{max} and then the logarithmic trapezoidal method will be used after t_{max} . The minimum requirement for the calculation of AUC will be the inclusion of at least three consecutive plasma concentrations above the lower limit of quantification (LLOQ), with at least one of these concentrations following C_{max} . AUC(0- ∞) values where the percentage of the total area extrapolated is more than 20% will be flagged. Any AUC(0- ∞) value excluded from summary statistics will be noted in the footnote of the summary table.
- Half-life ($t_{1/2}$) will be calculated, when appropriate, based on the apparent terminal log-linear portion of the concentration-time curve. The start of the terminal elimination

phase for each subject will be defined by visual inspection and generally will be the first point at which there is no systematic deviation from the log-linear decline in plasma concentrations. Half-life will only be calculated when a reliable estimate for this parameter can be obtained comprising of at least 3 data points. If $t_{1/2}$ is estimated over a time window of less than 2 half-lives, the values will be flagged in the data listings. Any $t_{1/2}$ value excluded from summary statistics will be documented in the footnote of the summary table.

- A uniform weighting scheme will be used in the regression analysis of the terminal log-linear portion of the concentration-time curve.
- The parameters based on observed last quantifiable drug concentration (C_{last}) will be reported.

Individual PK Parameter Rules

- Only quantifiable concentrations will be used to calculate PK parameters with the exception of special handling of certain concentrations reported below the lower limit of quantitation (BQL). Plasma concentrations reported as BQL will be set to a value of zero when both of the following conditions are met:
 - The samples are from the initial dose period for a subject or from a subsequent dose period following a suitable wash-out period.
 - The time points occur before the first quantifiable concentration.
- All other concentrations BQL that do not meet the above criteria will be set to missing.
- Also, where two or more consecutive concentrations are BQL towards the end of a profile, the profile will be deemed to have terminated and any further quantifiable concentrations will be set to missing for the calculation of the PK parameters.

Individual Concentration vs. Time Profiles

- Individual concentrations will be plotted using actual sampling times.
- The terminal point selections will be indicated on a semi-logarithmic plot.

Average Concentration vs. Time Profiles

- The average concentration profiles will be graphed using nominal sampling times.
- The average concentration profiles will be graphed using arithmetic mean concentrations.

- The predose average concentration will be set to zero. Otherwise, only quantifiable concentrations will be used to calculate average concentrations.
- Concentrations at a sampling time exceeding $\pm 10\%$ of the nominal sampling time will be excluded from the average concentration profiles.
- Concentrations excluded from the mean calculation will be documented in the final study report.
- A concentration average will be plotted for a given sampling time only if 2/3 of the individual data at the time point have quantifiable measurements and were collected within $\pm 10\%$ of the nominal sampling time.

Treatment of Outliers during Pharmacokinetic Analysis

This procedure provides justification for excluding data when scientifically appropriate. This procedure describes the methodology for identifying an individual value as an outlier for potential exclusion, but does not require that the value be excluded from analysis. The following methodology will not be used to exclude complete profiles from analysis.

Data within an Individual Profile

A value within an individual profile may be excluded from analysis if any of the following criteria are met:

- For PK profiles during single dosing of non-endogenous compounds, the concentration in a predose sample is quantifiable.
- For any questionable datum that does not satisfy the above criterion, the profile will be evaluated and results reported with and without the suspected datum.

Data between Individual Profiles

1. If $n < 6$, then the dataset is too small to conduct a reliable range test. Data will be analyzed with and without the atypical value, and both sets of results will be reported.
2. If $n \geq 6$, then an objective outlier test will be used to compare the atypical value to other values included in that calculation:
 - a. Transform all values in the calculation to the logarithmic domain.
 - b. Find the most extreme value from the arithmetic mean of the log transformed values and exclude that value from the dataset.
 - c. Calculate the lower and upper bounds of the range defined by the arithmetic mean $\pm 3 \times SD$ of the remaining log-transformed values.
 - d. If the extreme value is within the range of arithmetic mean $\pm 3 \times SD$, then it is not an outlier and will be retained in the dataset.

e. If the extreme value is outside the range of arithmetic mean $\pm 3*SD$, then it is an outlier and will be excluded from analysis.

If the remaining dataset contains another atypical datum suspected to be an outlier and $n \geq 6$ following the exclusion, then repeat step 2 above. This evaluation may be repeated as many times as necessary, excluding only one suspected outlier in each iteration, until all data remaining in the dataset fall within the range of arithmetic mean $\pm 3*SD$ of the log-transformed values.

Reporting of Excluded Values

Individual values excluded as outliers will be documented in the final report. Approval of the final report will connote approval of the exclusion.

9.3.2 Pharmacokinetic Statistical Methodology

PK parameters will be evaluated to delineate the effects of baricitinib formulation. For the primary analysis, log-transformed C_{max} , $AUC(0-t_{last})$, and $AUC(0-\infty)$ estimates will be evaluated in a linear mixed effects model with fixed effects for formulation, period, sequence, and a random effect for subject (sequence). The treatment differences between each test compared to the reference formulation will be back-transformed to present the ratios of geometric least squares (LS) means and the corresponding CIs. The Holm step-down procedure for an overall 0.1 alpha level will be used. This analysis applies only to Part A.

Bioequivalence between the suspension formulation administered either with or without water and the commercial tablet will be concluded if the 95% CI for C_{max} , $AUC(0-t_{last})$, and $AUC(0-\infty)$ are all completely contained within the interval (0.80, 1.25). If at least one of the administrations has all three 95% CIs contained within the interval (0.8, 1.25), then the second administration will be declared bioequivalent if the 90% CIs for C_{max} , $AUC(0-t_{last})$, and $AUC(0-\infty)$ are all completely contained within the interval (0.80, 1.25). The following comparisons shall be made:

- 4 mg baricitinib suspension with 240 mL water (fasted) vs 4 mg baricitinib tablet with 240 mL water (fasted)
- 4 mg baricitinib suspension without water (fasted) vs 4 mg baricitinib tablet with 240 mL water (fasted)

Example SAS code is provided below.

```
proc mixed data=dataset;
class subject group period sequence;
model l&var=group period sequence / cl solution outpred=resids;
random intercept / subject=subject(sequence);
lsmeans group / pdiff cl;
ods output lsmeans=lsmeans;
ods output diff=diffs;
run;
quit;
```

The same model will be used to compare the relative bioavailability of the suspension formulation administered with (test) and without (reference) water, with a significance level of 0.1. This analysis applies to Part A.

To determine the effect of a high-fat, high-calorie meal on the PK of baricitinib when administered as a single 4 mg dose of the suspension formulation, the ratio of geometric LS means between the fasted and fed states for C_{max} , $AUC(0-t_{last})$, and $AUC(0-\infty)$ will be evaluated. A linear mixed effects model with fixed effects for fasted/fed status, period, sequence, and a random effect for subject (sequence) will be used. The treatment differences between each fasted and fed state will be back-transformed to present the ratios of geometric LS means and the corresponding 90% CIs. This analysis applies to Part B.

The t_{max} will be analyzed using a Wilcoxon signed rank test for the comparisons listed above and for fasted vs fed for each study part. Estimates of the median difference based on the observed medians, 95/90% CIs, and p-values from the Wilcoxon test will be calculated.

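### Does the example SAS code in SAP 9.3.2 put the 90% intervals or the direction of the ratios at risk?

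*SAP*

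**What the plan says.** SAP 9.3.2 sets the Part A rule in words. "The Holm step-down procedure for an overall 0.1 alpha level will be used". The first step uses 95% intervals: "Bioequivalence between the suspension formulation administered either with or without water and the commercial tablet will be concluded if the 95% CI for" all three parameters lie inside the limits. If one administration passes, "then the second administration will be declared bioequivalent if the 90% CIs" lie inside the same limits. Each test treatment is compared with the tablet as reference.

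The with/without-water comparison reuses the model but carries its own level and direction: "suspension formulation administered with (test) and without (reference) water, with a significance level of 0.1". For Part B the SAP describes a model with fasted/fed status as the treatment effect, and the differences are to be "back-transformed to present the ratios of geometric LS means and the corresponding 90% CIs". Protocol 10.3.2.2 likewise asks for 90% intervals in the secondary analyses.

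One code block follows the two test-versus-tablet comparisons, introduced by "Example SAS code is provided below". It declares "class subject group period sequence", requests comparisons with "lsmeans group / pdiff cl", and saves the least squares means and their differences as datasets. It contains no `ALPHA=` option, no `ESTIMATE` statement, no named control level and no exponentiation.

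**The concern.** PROC MIXED uses alpha 0.05 unless told otherwise, so the block prints 95% limits. Those serve the first Holm step only. Taken literally, the second step would also be judged at 95%, which turns Holm into plain Bonferroni, and the secondary comparisons would carry the wrong level.

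`PDIFF` also subtracts the later level from the earlier one. Under the labels and display order in SAP section 6 (R, T1, T2), the output would be R−T1, R−T2 and T1−T2, the reverse of the Part A wording. If the same code were reused for Part B it would give fasted minus fed, so a drop in exposure with food would appear as a ratio above 1.

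Three things would be at stake: the chance of declaring both administrations bioequivalent, the choice of administration for Part B that depends on it, and the reading of the reported ratios.

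**Working it through.** **Inputs.** Cmax intra-subject CV 16%, 20 completers, 90% power with a 95% interval, limits 0.80 and 1.25, 14 completers in Part B (SAP section 7). Three periods and three treatments in Part A (SAP section 5). The documents give no true ratio, so the ratios below are assumptions. The SAS defaults are software behaviour and are not stated in the documents.

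**1. The plan's own figure.** σ = √ln(1 + 0.16²) = 0.159, and the standard error of a difference is 0.159 × √(2/20) = 0.0503. Power for two one-sided tests at 0.025 each, integrated over the distribution of the residual variance:

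| True ratio | 18 df | 36 df |
|---|---|---|
| 0.95 | 89.7% | 91.4% |
| 1.05 | 90.5% | 92.1% |
| 1.00 | 97.4% | 98.2% |

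The stated 90% is reproduced with a true ratio about 5% away from 1. It was calculated with the 95% interval.

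**2. What the level changes.** With 36 df, the half-width on the log scale is t × 0.0503:

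- 95%: 0.102, a factor of 1.107. At the assumed CV, observed ratios from 0.886 to 1.129 pass.
- 90%: 0.0849, a factor of 1.089. Observed ratios from 0.871 to 1.148 pass.

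For Part B, assuming the same CV with 14 completers and 12 df, the factors are 1.140 and 1.113.

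**3. Cost if 95% limits were used at both steps.** Simulation of 400,000 trials, Cmax only, 36 df. The two log ratios share the reference mean, and each treatment mean has standard deviation 0.159/√20. Holm as written declares both bioequivalent when one passes at 95% and the other at 90%.

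| True ratios | Holm as written | 95% at both steps | Loss (points) |
|---|---|---|---|
| 1.00 / 1.00 | 98.7% | 96.6% | 2.1 |
| 0.95 / 0.95 | 91.9% | 85.6% | 6.4 |
| 0.95 / 1.05 | 91.6% | 83.5% | 8.1 |
| 1.00 / 0.90 | 73.9% | 61.6% | 12.3 |

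Losses are taken from the unrounded probabilities. The intervals are wider than the rule needs, so type I error is not inflated.

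**4. Direction.** ln 0.80 = −ln 1.25, so the limits are symmetric on the log scale and changing the sign of a difference cannot move it across them. Take an observed ratio of 0.88. At 90% the lower limit is 0.88/1.089 = 0.808, a pass. Inverted, 1/0.88 = 1.136 and the upper limit is 1.136 × 1.089 = 1.237, also a pass. At 95% both fail (0.88/1.107 = 0.795; 1.136 × 1.107 = 1.258). In the simulation, reversal changed none of the 400,000 decisions under any pair of ratios.

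**5. Text against code.**

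| Analysis | Level in the text | Direction in the text | Code supplied |
|---|---|---|---|
| Holm step 1 | 95% | test vs tablet | the example, level correct |
| Holm step 2 | 90% | test vs tablet | none at 90% |
| With vs without water | 0.1, hence 90% | with (test) vs without (reference) | none at 90% |
| Part B food effect | 90% | neither state named as reference | none |

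Every required level is stated. The saved differences hold the estimate, standard error and degrees of freedom, so 90% limits are estimate ± t(0.95, df) × SE with no refit. Since the block does not exponentiate, a later step has to process these differences anyway, and the sign is set there.

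**The case for a change.** The strongest argument for a change is that the SAP supersedes the protocol's statistical section and is the template for the study report, and this is the only inferential code it contains. A literal reading could also reach Part B. Suppose suspension with water passes at 95%, and suspension without water passes at 90% but not at 95%. The stated rule declares both bioequivalent, and SAP section 10 then gives Part B without water. A 95%-only analysis declares only the with-water administration and would select that one. At true ratios of 0.95 for both, this is by symmetry half of the 6.4-point gap, about 3 points on Cmax.

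That arithmetic is right, but it needs an analyst to set aside an explicit 90% rule printed just above the code in favour of a default in a block that uses placeholder dataset and variable names. SAP section 7 also computed power at 95% so that both comparisons would be adequately powered, so the sample size does not lean on the second-step gain.

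The direction argument is weaker. How the treatment variable is coded is not shown; SAP section 6 fixes abbreviations and display order, not the coding of the class variable. Part A's direction is given in words. For Part B the documents speak only of the ratio between the fasted and fed states, so fasted over fed contradicts nothing. The tablet's 18% fall in Cmax with food (Protocol 3.2) would then read 1/0.82 = 1.22, which is unambiguous once the ratio is labelled.

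What stands is that the example is incomplete: it shows neither the 90% limits nor the contrast direction.

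**Conclusion.** No change is called for. The example illustrates the first Holm step, and the text that governs the analysis gives the right level for every comparison and the direction for Part A. An analyst following the SAP reaches the intended intervals and decisions from the output the code already saves. More code would complete an illustration without altering a rule, an error rate or an estimate.

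The losses of 2 to 12 points arise only if the example is allowed to override the written rule. They concern Cmax alone, rest on assumed true ratios with CV 16% and 20 completers, and err on the conservative side. At the planned AUC CVs of 7.8% and 7.6%, power with a 95% interval is above 99% even at a true ratio of 0.90, so the level matters little there. Reversal depends on coding that the documents do not show, and it leaves every bioequivalence verdict unchanged.

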9.4 Safety and Tolerability Assessments

The following analyses will be done separately for Part A and Part B.

9.4.1 Adverse events

Where changes in severity are recorded in the Case Report Form (CRF), each separate severity of the AE will be reported in the listings, only the most severe will be used in the summary tables. A pre-existing condition is defined as an AE that starts before the subject has provided written informed consent and is ongoing at consent. A non-treatment emergent AE is defined as an AE which starts after informed consent but prior to dosing. A treatment-emergent AE is defined as an AE which occurs postdose or which is present prior to dosing and becomes more severe postdose.

All AEs will be listed. Treatment-emergent AEs will be summarized by treatment, severity and relationship to the study drug. The frequency (the number of AEs, the number of subjects experiencing an AE and the percentage of subjects experiencing an AE) of treatment-emergent AEs will be summarized by treatment, Medical Dictionary for Regulatory Activities (MedDRA) version 19.1 system organ class and preferred term. The summary and frequency AE tables will be presented for all causalities and those considered related to the study drug. Any serious AEs will be tabulated. Concomitant medication

Concomitant medication will be coded using the World Health Organization (WHO) drug dictionary (Version September 2016). Concomitant medication will be listed.

9.4.2 Clinical laboratory parameters

All clinical chemistry, hematology and urinalysis data will be listed. Additionally clinical chemistry, hematology and urinalysis data outside the reference ranges will be listed.

Values for any clinical chemistry, hematology and urinalysis values outside the reference ranges will be flagged on the individual subject data listings.

9.4.3 Vital signs

Vital signs data will be listed for individual subjects.

9.4.4 Electrocardiogram (ECG)

ECGs will be performed for safety monitoring purposes only and will not be presented.

9.4.5 Other assessments

All other safety assessments not detailed in this section will be listed but not summarized or statistically analyzed.

9.4.6 Safety and Tolerability Statistical Methodology

No inferential statistical analyses are planned.

10. INTERIM ANALYSES

A formal interim analysis of PK data will be performed after all PK data are available for Part A. Statistical analysis will be conducted to test the baricitinib suspension formulation, administered with and without water, for bioequivalence with the commercial tablet formulation. The dosing method for the suspension formulation that is bioequivalent to the commercial tablet formulation will be used in Part B. If both administration methods are bioequivalent to the commercial tablet formulation, suspension will be administered without water in Part B, for ease of administration. If the suspension formulation is not bioequivalent to the commercial tablet formulation using either administration method, all available data will be used to assess the most appropriate way to administer the drug in Part B.

Intra-subject variability estimates of PK parameters will be used to determine the number of subjects required to complete Part B of the study.

11. CHANGES FROM THE PROTOCOL SPECIFIED STATISTICAL ANALYSES

There were no changes from the protocol specified statistical analyses.

13. DATA PRESENTATION

13.1 Derived Parameters

Individual derived parameters (e.g. PK parameters) and appropriate summary statistics will be reported to three significant figures. Observed concentration data, e.g. C_{max} , should be reported

as received. Observed time data, e.g. t_{max} , should be reported as received. N and percentage values should be reported as whole numbers. Median values should be treated as an observed parameter and reported to the same number of decimal places as minimum and maximum values.

13.2 Missing Data

Missing data will not be displayed in listings.

